14.0 AUDITING

As coordinating center of this trial, Washington University (via the Quality Assurance and Safety Monitoring Committee (QASMC) will monitor each participating site to ensure that all protocol requirements are being met; that applicable federal regulations are being followed; and that best practices for patient safety and data collection are being followed per protocol. Participating sites will be asked to send copies of all audit materials, including source documentation. The audit notification will be sent to the Washington University Research Patient Coordinator, who will obtain the audit materials from the participating institution.

Notification of an upcoming audit will be sent to the research team one month ahead of the audit. Once accrual numbers are confirmed, and approximately 30 days prior to the audit, a list of the cases selected for review (up to 10 for each site) will be sent to the research team. However, if during the audit the need arises to review cases not initially selected, the research team will be asked to provide the additional charts within two working days.

Items to be evaluated include:

- Subject screening and enrollment
- Reporting of adverse events
- Maintenance of HIPAA compliance
- Completeness of regulatory documentation
- Completeness of participant documentation
- Acquisition of informed consent
- IRB documentation
- Issues of protocol adherence

Additional details regarding the auditing policies and procedures can be found at <https://siteman.wustl.edu/wp-content/uploads/2015/10/QASMC-Policies-and-Procedures-03.31.2015.pdf>

15.0 STATISTICAL CONSIDERATIONS

15.1 Power Analysis

In the phase I portion of the study, a traditional 3+3 design is used to determine the maximal tolerated dose (MTD) of MK-3475 when combined with MLA for the treatment of recurrent malignant gliomas.

Power analysis for phase II is based on PFS. Using a 1-sided alpha of 0.15, with an accrual interval of 20 months and additional follow-up of 6 months (study period in Phase II is 26 months), and assuming a progression free survival probability at 6 month (6-PFS) of 40% for the MK-3475 alone group and 65% for MK-3475 + MLA combination group, we will need 17 patients per group with probability (power) 0.8. If the 6-PFS of the MK-3475 alone group is 45% and 65% for the MK-3475 + MLA combination group, we will need 25 patients per group. We are planning to enroll 20 patients per group for the phase II portion of trial.

6-PFS in MK-3475 alone group	6-PFS in MK-3475 + MLA combination group	Sample per group
40%	50%	108
	55%	48
	60%	27
	65%	17
45%	55%	105
	60%	46
	65%	25
	70%	16
50%	60%	100
	65%	43
	70%	24
	75%	15
55%	65%	93
	70%	40
	75%	21
	80%	13
60%	70%	84
	75%	35
	80%	19
	85%	11

Six-PFS for all current commonly used treatments for recurrent GBM (e.g. bevacizumab, temozolomide, carboplatin, carmustine, lomustine, etoposide, irinotecan) ranges from < 10% to low 30%³⁹⁻⁴³. Since historical data on 6-PFS in recurrent GBM for both MK-3475 and MLA are not available, for the purpose of reasonable estimation of efficacy of the MK-3475 and MLA combination as compared to MK-3475 alone in recurrent/progressive

GBM, we will assume that the 6-PFS of the MK-3475 alone group to be 40-45% to derive sample size estimates for both groups as detailed above.

15.2 Analysis Plan

PFS and OS will be estimated by Kaplan-Meier product limit method and the difference in PFS with recurrent GBM being treated with MK-3475 alone vs. those being treated with MK-3475 plus MLA will be compared by log-rank test.

Two-group t-test will be used to compare the anti-glioma immune response before and after MK-3475 with or without MLA.

Cox proportional hazard model will be used to determine the relationship between intratumoral expression of PD-L1, the frequency of glioma cell-specific cytotoxic T cells with PFS and OS while proportional hazard assumption will be examined.

Pearson correlation coefficient (r) will be calculated between intratumoral expression of PD-L1 and the frequency of glioma cell-specific cytotoxic T cells. Similarly, Cox proportional hazard model will be used to investigate the relationship between PD-1-dependent biomarkers in glioma cell-specific T cells and PFS and OS.

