15.4 Interim Analysis

Per DSMC request, an interim analysis was conducted in June 2019. The MK-3475 + MLA group included 2 GBM patients who received 200mg in Phase 1 and 10 patients in Phase 2. PFS probability at 6, 9, and 12 months after treatment are 45.0%, 45.0%, and 33.8%, the median PFS is 5.49 months. Survival probabilities at 6, 9, and 12 months after treatment are 75.0%, 62.5%, and 50.0%, and the median OS is not estimable. For the MK-3475 monotherapy (no MLA) group, PFS probability at 3 months after treatment is 44.4%

and the median PFS is 2.73 months (95% CI: 1.41-3.88). Survival probabilities at 3 and 6 months after treatment are 83.3%, and 31.3%, and the median OS is 4.77 months (95% CI: 1.74-8.78).

This analysis showed significant differences in PFS and survival probabilities between the MK-3475 + MLA group and the MK-3475 alone group. Therefore, with Amendment 12, we are revising the study to a single arm (MK-3475 + MLA) in the spirit of minimizing harm, potential or perceived, to subjects and to complete the study in a timely manner. The recent study⁴⁶ shows median PFS was 2.4 months. To be conservative, we will use the shorter mPFS for MK-3475 + MLA group and longer mPFS from historical data. We will enroll additional 27 patients and expect 20 GBM patients will be evaluable for this study. With an accrual interval of 20 months and additional follow-up of 6 months, a two-sided, one-sample logrank test calculated from a sample of 32 subjects achieves 80.9% power at a 0.05 significance level to detect a median PFS of 5.1 months in the MK-3475 + MLA group when the median PFS of the historical control is 2.9 months.

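### After Amendment 12, Section 15.2 still prescribes a two-group log-rank test for PFS, while the 80.9% power in 15.4 belongs only to a one-sample test against a historical median of 2.9 months

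*Combined protocol and SAP*

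**What the plan says.** **Section 15.2 (Analysis Plan).** PFS and OS are estimated by Kaplan-Meier. PFS in patients "being treated with MK-3475 alone vs. those being treated with MK-3475 plus MLA will be compared by log-rank test". No alpha, sidedness, reference median or analysis set is given, and neither a historical control nor a one-sample test is mentioned. The immune-response analysis also keeps the two-arm wording: "Two-group t-test will be used to compare the anti-glioma immune response before and after MK-3475 with or without MLA". The Cox models in 15.2 relate biomarkers to PFS and OS and do not test treatment.

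**Section 15.1 (Power Analysis).** The Phase II design is two-group: "Using a 1-sided alpha of 0.15, with an accrual interval of 20 months" and 6 months of further follow-up. It ends: "We are planning to enroll 20 patients per group for the phase II portion of trial". Nothing marks this as replaced.

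**Sections 1.7, 4.4 and 10.2.2.** Amendment 12 stops randomization, closes the MK-3475-alone arm to new patients, and moves the survival comparison to historical data. The Schema gives the current Phase II size as 32 evaluable patients.

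**Section 15.4 (Interim Analysis).** With 20 months of accrual and 6 of follow-up, "a two-sided, one-sample logrank test calculated from a sample of 32 subjects achieves 80.9% power at a 0.05 significance level", for a median PFS of 5.1 months against a historical 2.9 months. The choice of medians is described as conservative: "we will use the shorter mPFS for MK-3475 + MLA group and longer mPFS from historical data".

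**The concern.** The primary Phase II endpoint is PFS (Section 2.1). The section that tells the analyst what to run names one treatment test, and the section that justifies the sample size names another. They differ in comparator (the closed concurrent arm or a fixed historical median), in number of groups, and in the patients used. The alphas attached to the two designs also differ (one-sided 0.15 in 15.1, two-sided 0.05 in 15.4).

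An analyst who follows 15.2 literally would compare the combination arm with the patients treated with MK-3475 alone before the arm closed, and would report a test to which the stated 80.9% does not apply. Because 15.2 states no alpha, that analyst would turn to 15.1, which still offers the threshold of the abandoned design. The choice of test and threshold for the primary endpoint should be fixed in the analysis plan before the data are analysed.

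**Working it through.** **Inputs.** From 15.4: n = 32, medians 5.1 and 2.9 months, accrual 20 months, follow-up 6 months, two-sided 0.05. From 15.1: one-sided 0.15, power 0.8, 6-month PFS 40% or 45% against 65%. Assumed: exponential PFS and uniform accrual, which the documents do not state.

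**Step 1. Hazards and event probabilities.** λ = ln 2 / median, so λ1 = 0.1359 (5.1 months) and λ0 = 0.2390 (2.9 months). HR = 2.9/5.1 = 0.569.

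The probability of an observed event is p = 1 − [exp(−6λ) − exp(−26λ)] / (20λ), giving p1 = 0.848 and p0 = 0.951.

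**Step 2. The plan's own figure (15.4).** For the one-sample log-rank, O is the number of events and E the cumulative null hazard summed over patients. Under the alternative:

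- O = 32 × 0.848 = 27.1
- E = O × λ0/λ1 = 47.7, or 1.491 per patient
- mean shift per patient = 1.491 − 0.848 = 0.643
- variance of O − E per patient under the alternative = 2.038; null variance = 1.491

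Power = Φ[(√32 × 0.643 − 1.960 × √1.491) / √2.038] = Φ[(3.639 − 2.393) / 1.428] = Φ(0.872) = **80.9%** (0.8085), as stated. Other variance conventions give higher values, for example 83.7% to 85.6%, and simulation gives 84.0%, so the stated figure is not optimistic.

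**Step 3. The 15.1 figures for their own design.** Schoenfeld events for equal groups: d = 4(1.036 + 0.842)² / (ln HR)².

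- 40% vs 65%: HR = ln 0.65 / ln 0.40 = 0.470, d = 25, 16.3 per group, so 17 (stated 17).
- 45% vs 65%: HR = 0.539, d = 38, 25.4 per group (stated 25).

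Each section is arithmetically sound for the design it describes, but the designs are different.

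**Step 4. The test in 15.2, with the medians of 15.4.** Take 32 combination patients against k patients on MK-3475 alone. The documents do not give k, so 6 to 20 is assumed; 20 is the full planned arm.

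d = 32 × 0.848 + k × 0.951, a = 32/(32 + k), power = Φ[0.5645 × √(d·a(1 − a)) − z], where 0.5645 = |ln 0.569|.

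| k (assumed) | events d | power, two-sided 0.05 | power, one-sided 0.15 |
|---|---|---|---|
| 6 | 32.8 | 21.8% | 55.7% |
| 10 | 36.6 | 30.7% | 66.2% |
| 15 | 41.4 | 39.5% | 74.4% |
| 20 | 46.1 | 46.2% | 79.7% |

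Simulated log-rank tests give 28% to 47% at two-sided 0.05 and 61% to 80% at one-sided 0.15 over the same range.

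**The case against.** The strongest reply is that nothing is missing from the protocol. Section 15.4 gives the test, sidedness, alpha, sample size, null and target, and says that the study is being revised to a single arm. Sections 1.7 and 2.2 name historical data as the comparator. On this view the defect is one of placement.

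That is right about intent, and it limits the severity. It does not remove the contradiction: 15.4 is headed Interim Analysis and states the test only as a power calculation, 15.2 is the analysis plan and prescribes something else, and neither 15.1 nor 15.2 is marked as replaced.

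Other parts of the reply stand, and they rule out some stronger readings that a reader might infer:

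- **That the 80.9% is wrong.** It is not; it reproduces for the test in 15.4.
- **That two alphas compete for one analysis.** Each belongs to its own design, and 15.4 says which design is the revision. The fault is the missing label on 15.1.
- **That the control rate in 15.1 contradicts 15.4.** Section 15.1 says "we will assume that the 6-PFS of the MK-3475 alone group to be 40-45" per cent, and 15.4 reports 45.0% at 6 months for the combination. But 15.1 calls its figure an assumption made because historical data were lacking. An assumption overtaken by later data is not a contradiction.
- **That 15.2 cannot be carried out.** Patients were treated with MK-3475 alone before Amendment 12, and 15.4 already compares the two groups. The test can be run; it is not the powered one.
- **That 2.9 months is unfounded.** Section 15.4 quotes 2.4 months from reference 46 and does not say where 2.9 comes from, while 1.7 points to references 44 to 46. That supports asking for a citation, no more.

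**Conclusion.** The plan is wrong as written and should be corrected. The only treatment comparison of PFS in 15.2 belongs to the design that Amendment 12 ended, and the Phase II design in 15.1 stands unmarked beside its replacement. The stated power belongs solely to the one-sample test in 15.4.

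That the 80.9% does not transfer follows from the difference between the tests. The size of the gap is an illustration only: about 22% to 46% at two-sided 0.05 against 80.9%. It rests on an assumed 6 to 20 patients on MK-3475 alone, exponential PFS, the same 20 + 6 month accrual and follow-up for both groups, and the historical 2.9 months for the alone arm, although 15.4 reports 2.73 for the trial's own. The 81% reproduction also rests on exponential PFS.

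The intended analysis can be recovered from 1.7 and 15.4, so this is a should-fix inconsistency and does not show that the revised design is unsound.

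**What to change.** 1. In 15.2, replace the two-group log-rank with the 15.4 test as the PFS hypothesis test: a one-sample log-rank of the 32 evaluable MK-3475 + MLA GBM patients against a historical median PFS of 2.9 months, at two-sided 0.05.
2. State the reference survival curve that the sponsor used for the 80.9%. An exponential curve reproduces it, but the documents name none, so the sponsor should confirm it. Cite the source of 2.9 months at the same place.
3. Label any comparison with the closed MK-3475-alone arm, including the immune-response t-test with or without MLA, as supportive or descriptive.
4. In 15.1, mark the Phase II alpha, the sample-size table and the 20 per group as superseded by Amendment 12, and refer to 15.4 for the current basis.

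The cost is wording in two sections and one citation. It needs no more patients, no new data and no analysis beyond the one that 15.4 already powers.

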1.6 Correlative Studies Background

In both arms of phase II, intratumoral PD-L1 expression will be determined by qRT-PCR and/or IHC. TIL profile will be assessed by flow and mass spectrometry or IHC to compare to the profile at initial surgery prior to recurrence (when available). Glioma-specific immune response will be assessed in cultured TIL, peripheral blood, and sampled cLN (where available). Pre- and post-surgery peripheral blood will be assessed by flow cytometry through the Center for Human Immunology and Immunotherapy immune monitoring core (for Washington University samples) and the [name] lab or the University of Florida Brain Tumor Immunotherapy Program (for the UF samples) for markers of T cell activation and anergy as well as cytokine profiles. In addition, PD-1-dependent signature in glioma cell-specific T cells from the peripheral blood and sampled cLN where samples and RNAseq are available can be generated by novel RNAseq methodology developed at Washington University and University of Florida in order to characterize the PD-1-dependent transcriptional signatures and develop a PD-1 dependent biomarker program that will be easily de-convoluted to provide data on serial changes in (a) cell type composition and (b) cell type activation programs. Furthermore, if necessary, serum or plasma will be assessed for the presence and level of soluble immune checkpoint molecules, cytokines, and chemokines using commercially available multiplex immunoassays.

1.7 Rationale for Amendment 12

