2.2 Secondary Objectives

1. Phase I: To determine the toxicity profile of MK-3475 in combination with MLA for the treatment of recurrent malignant gliomas.
2. Phase II: To determine the overall survival (OS) of patients with recurrent GBM, WHO grade IV being treated with MK-3475 plus MLA as compared to historical controls treated with MK-3475 alone.
3. Phase II: To assess the anti-glioma immune response before and after MK-3475 with MLA.
4. Phase II: To correlate intratumoral expression of PD-L1 and the frequency of glioma cell-specific cytotoxic T cells with PFS and OS.
5. Phase II: To identify PD-1-dependent biomarkers in glioma cell-specific T cells that negatively correlate with the frequency of glioma cell-specific cytotoxic T cells and PFS and OS.

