For all phase II patients, research blood will be drawn prior to MLA and immediately prior to the first dose of MK-3475. Subsequently, research blood will be drawn at doses 2, 4, 6, 9, 18, 36, and at the end of treatment. In addition, an optional ipsilateral cervical lymph node may be sampled by FNA prior to or at the time of surgical procedure (including surgical debulking, MLA, or biopsy) and again 6 weeks after surgery. Those patients who, in the event of surgical intervention for clinical reasons of a radiographically progressing tumor, undergo a subsequent surgical procedure (whether biopsy or resection) will have tissue collected for correlative analysis after histopathologic diagnosis of recurrent GBM.

Additionally, for patients enrolled to phase II who have surgical intervention for a radiographically progressing tumor but subsequent surgical pathology demonstrating a predominant immune-mediated reaction **with no obvious progression of tumor**, such subjects will be deemed not to have progressed and be allowed to resume assigned study treatment at a time deemed safe by the treating physician, but no later than 8 weeks from the surgery.

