9.0 CORRELATIVE STUDIES

The collections for correlative studies are for patients enrolled in phase II only unless otherwise indicated.

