9.1 Blood Specimens

9.1.1 Collection of Specimens

Forty mL of blood will be collected into 4 pink top tubes (with EDTA) for isolation of PBMCs at the following time points **for Phase II patients only**:

- No more than one week prior to surgical procedure (including resection/debulking, MLA or biopsy)
- No more than 3 days prior to the first dose of MK-3475
- No more than 7 days prior to the second dose of MK-3475 and at doses 4, 6, 9, 18, and 36
- At the end of treatment visit

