9.2 Cervical Lymph Node Samples - OPTIONAL

9.2.1 Collection of Specimens

Ipsilateral cervical lymph nodes of all phase II patients will be sampled by FNA (regardless of whether the node is pathologically enlarged) at the following time points:

- Time of surgical resection/debulking or biopsy or MLA/biopsy
- 6 weeks +/- 1 week after surgical resection/debulking or biopsy or MLA/biopsy (if tumor-specific precursor frequency in PBMC is low)

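### The two-group t-test in Section 15.2 does not fit the within-patient before/after immune comparison in secondary objective 3, and no paired or repeated-measures method is named

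*Combined protocol and SAP*

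**What the plan says.** Section 15.2 (Analysis Plan) gives one sentence on this endpoint: "Two-group t-test will be used to compare the anti-glioma immune response before and after MK-3475 with or without MLA".

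Section 2.2 words secondary objective 3 as "To assess the anti-glioma immune response before and after MK-3475 with MLA". Since Amendment 12 (Sections 1.7 and 4.4), phase II has been a single MK-3475 + MLA arm.

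The blood samples are serial. Section 5.0 states that, for all phase II patients, "research blood will be drawn prior to MLA and immediately prior to the first dose of MK-3475". Section 9.1.1 continues with "No more than 7 days prior to the second dose of MK-3475 and at doses 4, 6, 9, 18, and 36", plus an end-of-treatment draw. Section 9.0 adds: "The collections for correlative studies are for patients enrolled in phase II only unless otherwise indicated".

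The other specimens are less regular. Section 1.6 compares the tumor-infiltrating lymphocyte (TIL) profile with that at the initial surgery only where the earlier material exists. Section 9.2 makes lymph-node sampling optional and takes the second sample only "if tumor-specific precursor frequency in PBMC is low".

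Section 15 names no paired test, signed-rank test, change score or mixed model.

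**The concern.** The before and after blood values come from the same patients, so they are paired. A two-group t-test treats them as two independent samples. Its standard error leaves out the covariance between a patient's two values, and with positive correlation that standard error is too large. The test then rejects less often than its nominal level under no change, and it loses power when there is a change.

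What is at stake is the readout of immune change under the combination. Section 1.5 rests the trial on immune activation, and the plan asks each patient for up to nine blood draws to study it. A test that discards the pairing wastes much of that information. The plan also does not say which of the post-dose draws counts as after, or whether the pre-procedure or the pre-dose-1 draw counts as before.

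**Working it through.** **1. Is there a figure in the plan to reproduce?** No. Section 15 gives no effect size, standard deviation, correlation, alpha or power for the immune response. The power statements in Sections 15.1 and 15.4 concern PFS only. The calculation below is therefore illustrative.

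**2. How many patients can contribute pairs?** Section 15.4 says: "The MK-3475 + MLA group included 2 GBM patients who received 200mg in Phase 1 and 10 patients in Phase 2". It expects 20 more evaluable patients. That gives 2 + 10 + 20 = 32, the number used for the PFS power. Correlative collections are for phase II only, so the 2 phase I patients have no planned research blood: 10 + 20 = 30. This assumes a usable pair from every evaluable patient. A case with 20 complete pairs is shown as well.

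**3. Standard errors.** Let σ be the SD at each time, ρ the within-patient correlation and n the number of pairs.
- True variance of the mean change: 2σ²(1 − ρ)/n.
- Variance the two-group test estimates: 2σ²/n.
- Ratio of standard errors: 1/√(1 − ρ), which is 1.20 at ρ = 0.3, 1.41 at 0.5 and 1.83 at 0.7.

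**4. Power and size.** Two-sided 0.05 is assumed; d is the change in SD units.
- Paired test: noncentral t with n − 1 degrees of freedom and noncentrality d√n/√(2(1 − ρ)). For n = 30, d = 0.5, ρ = 0.5 this is 0.5 × 5.477/1 = 2.74, giving 75% power.
- Two-group test: simulated bivariate normal pairs, pooled t with 2n − 2 degrees of freedom (300,000 runs for power, 1.5 million for size).

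| n | d | ρ | Paired power | Two-group power |
|---|---|---|---|---|
| 30 | 0.5 | 0.02 | 47% | 48% |
| 30 | 0.5 | 0.3 | 61% | 47% |
| 30 | 0.5 | 0.5 | 75% | 47% |
| 30 | 0.5 | 0.7 | 93% | 47% |
| 30 | 0.8 | 0.5 | 99% | 93% |
| 20 | 0.5 | 0.5 | 56% | 29% |
| 20 | 0.8 | 0.5 | 92% | 76% |

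Actual type I error of the two-group test at n = 30, nominal 5%: 5.0% at ρ = 0, 2.0% at 0.3, 0.7% at 0.5 and 0.07% at 0.7. At n = 30 and d = 0.5 the two power curves cross at ρ of about 0.03 to 0.05; below that the two-group test is marginally better because it has more degrees of freedom.

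**5. The two readings of the sentence.**
- Before values against after values: the samples are paired, and the named test does not suit them.
- Change with MLA against change without MLA: a two-group t-test on change scores is valid. But no change score is named, the arm without MLA is closed to new patients (Section 10.2.2), and the contrast is not objective 3 as now worded.

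Under either reading, objective 3 has no suitable stated method.

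**The case against.** The strongest reply is that the sentence was written for two randomised arms, that the reference to treatment with and without MLA names two groups, and that a two-group t-test on change between them is sound. On that view the fault is only that Section 15.2 was not updated after Amendment 12. This stands as an account of how the sentence may have arisen, and the plan does not say outright that raw values will be compared. It does not supply a method for objective 3.

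A second point also stands. The rationale in Section 1.5 is synergy between MLA and MK-3475, and a before/after comparison in one combined-treatment arm cannot separate their contributions. The between-arm comparison bears more directly on that question. However, that arm is closed and Section 15.4 does not give its size, so descriptive use is reasonable. The cost should be acknowledged.

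Third, the endpoint is secondary and unpowered, the objective speaks of assessing rather than testing, and the power figures rest wholly on assumed values. All true. They limit the weight of the point and leave the mismatch in place.

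Finally, treatment stops at confirmed progression (Section 5.9), so the later dose-linked draws come only from patients still on treatment. A mixed model uses incomplete series, but it does not by itself remove bias if missingness depends on unobserved immune values. That caution is fair and is carried into the fix.

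**Conclusion.** The point holds. The only test named for the immune response does not suit the within-patient comparison that objective 3 now asks for, and nothing elsewhere in the plan fills the gap. The conclusion is firm for blood, where pairing is scheduled. It does not extend to TIL and lymph-node measures, for which complete pairs may be few.

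If the test is applied to raw before and after values, the cost is lost power: at n = 30 and a 0.5 SD change, 14 percentage points at correlation 0.3, 28 at 0.5 and 46 at 0.7. The cost is nil at correlation near 0, and about 6 points at 0.8 SD and correlation 0.5. These sizes assume two-sided 0.05, equal SDs, normal data and a complete pair from every patient. With positive correlation the error is conservative, so it adds no false positives. The primary PFS analysis and safety monitoring are untouched. The text should be corrected, but this is not a threat to the trial's main conclusion.

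**What to change.** Replace the sentence in Section 15.2 with a within-patient method for the serial blood measures:

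- **Main analysis:** a paired t-test, or a Wilcoxon signed-rank test, on the change from the pre-procedure sample to one named post-dose sample. The investigators should name that draw in advance. An early draw will lose fewer patients to progression.
- **Alternative:** a mixed model with a patient random effect over the scheduled draws, which keeps patients with incomplete pairs. State the assumption made about draws missing because treatment stopped, and report the number of patients at each draw.
- **Between arms:** keep the two-group t-test only for a descriptive comparison of change scores that includes the patients randomised to MK-3475 alone before Amendment 12.
- **Tissue and lymph nodes:** report descriptively, with the number of complete pairs.

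The cost is a few sentences in the analysis plan. Samples, patients and software stay the same.
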